8.7 Adjustment of Dose and/or Treatment Schedule

Adjustment of dose is not permitted.

8.7.1 Delay in Vaccination

If any of the following events occur within 72 hours of the day planned for study vaccination, the subject experiencing these symptoms should not receive the study vaccine:

- Acute illness, as determined by the Investigator, with or without fever
- Fever, defined as temperature $\geq 38.0^{\circ}\text{C}$ (100.4°F)

As long as the subject remains eligible for study participation, the fever has subsided and/or the moderate or severe infection has resolved or reduced to mild severity for 48 hours, and the subject has been tested and confirmed to be negative for the SARS-CoV-2 virus, as appropriate (Section [6.2.4](#)) the study vaccination may be rescheduled.

8.8 Withdrawal of Subjects from the Study Procedures

Subjects must be withdrawn from study procedures for any of the following:

- Withdrawal of consent
- The subject is unwilling or unable to comply with the protocol in the judgement of the Investigator

Other reasons for withdrawal of subjects from study procedures might include:

- At the discretion of the Investigator for medical reasons
- Significant protocol deviation
- The subject is lost to follow-up

All efforts will be made to complete and report the observations as thoroughly as possible up to the date of withdrawal. All information, including the reason for withdrawal from study, must be recorded in the eCRF.

For subjects who fail to show up for the final visit, or for three consecutive visits, study staff are encouraged to make at least three documented attempts to contact the subject by telephone and at least one documented written attempt to contact the subject or legal guardian to encourage the completion of study termination procedures. These efforts to contact the subject should be recorded in the source documentation. The termination date for the subject to be captured on the Study Termination eCRF page is the date of the last successful contact (clinic visit or telephone) with the subject. These subjects will be regarded as lost to follow-up.

Any subject who withdraws consent to participate in the study will be removed from further treatment and study observation immediately upon the date of request. These subjects should be encouraged to complete the early termination study procedures and observations at the time of withdrawal ([Appendix 1](#)).

For subjects withdrawn for reasons other than withdrawal of consent every effort should be made to complete the early termination of study procedures and observations at the time of withdrawal (see [Appendix 1](#)).

The reason for withdrawal from the study will be entered in the EDC. If the reason for withdrawal includes one or more AEs then an AE will be entered as the primary reason for withdrawal.

8.9 Concomitant Therapy and Procedures

The use of concomitant therapies or procedures defined below must be recorded on the subject's eCRF. Adverse events associated with administration of these therapies or procedures must also be documented on the appropriate eCRF.

8.9.1 Concomitant Therapy

A concomitant therapy is any non-protocol specified drug or substance (including over-the-counter medications, herbal medications and vitamin supplements) administered between signing of the informed consent document and the subject's last protocol-specified study visit.

Disallowed Concomitant Therapy

The use of the following concomitant medications and/or vaccines will not require withdrawal of the subject from the study but may determine a subject's eligibility in the per-protocol analysis:

- Any investigational or non-registered product (drug or vaccine) other than the study vaccine used during the study period.
- A non-study live, attenuated vaccine administered during the period from 28 days before through 28 days after each dose of study vaccine or any approved inactivated or recombinant vaccine that was administered within 14 days before or after any dose of study.
- Immunoglobulins and/or any blood products administered during the study period (except for treatment of COVID-19).
- Medications that suppress the immune system, including corticosteroids administered at doses of 20 mg prednisone equivalent/day or higher, with the exception of medications used in the treatment of COVID-19.

Subjects who receive ARCT-021 vaccine in this study should also be asked if they have taken any antipyretic or analgesic to prevent fever or pain within 24 hours prior to vaccine administration or if they have taken antipyretic or analgesics to treat fever or other solicited adverse events within 7 days after each study vaccine administration, including the day of dosing. These details should be specified on the Concomitant Medication CRF page.

All medication and interventions necessary for the appropriate care for the study participant, particularly to treat COVID-19, should be administered and appropriately documented along with the adverse event.

All concomitant medications must be recorded in the eCRF until 28 days after the dose of ARCT-021 (if relevant). Otherwise, only concomitant medications associated with an SAE, CESI, NOCD or MAAE or for treatment of COVID-19 will be entered in the eCRF.

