5.2 Exclusion Criteria

1. Significant (as determined by Principal Investigator) noncompliance with the study visits or procedures in Study ARCT-021-01
2. Any subject that received placebo in the Parent Study and who is not willing to receive ARCT-021 in this study.

Only for subjects that will receive ARCT-021 in this study:

- 3 Receipt of any other SARS CoV-2 or other experimental coronavirus vaccine since completion of the Parent Study or planned during this study.

4. Diagnosis of new clinically significant abnormalities in medical history or physical examination since enrolment in the Parent Study, including but not limited to:
 - Respiratory disease (e.g., chronic obstructive pulmonary disease [COPD], asthma) requiring daily medications or oxygen currently or any treatment of respiratory disease exacerbations (e.g., COPD or asthma exacerbation) warranting hospitalization or an emergency room visit or supplemental oxygen.
 - Significant cardiovascular disease (e.g., congestive heart failure, cardiomyopathy, ischemic heart disease), myocarditis or pericarditis.
 - Neurological or neurodevelopmental conditions (e.g., migraines, epilepsy, stroke, seizures, encephalopathy, focal neurologic deficits, Guillain-Barré syndrome, encephalomyelitis or transverse myelitis).
 - New diagnosis of a significant hematologic abnormality (e.g., sickle cell disease, beta thalassemia)
 - New Diagnosis of autoimmune disease as listed by the American Autoimmune Related Disease Association ([Appendix 3](#))
 - Major surgery
5. Screening laboratory results as follows, or any other clinically significant abnormalities in screening laboratory values that would render a subject unsuitable for inclusion
 - ALT, AST, GGT, total bilirubin or alkaline phosphatase, > ULN unless approved by Sponsor Medical Monitor (or designee).
 - Hb <10 g/dL for females and <12 g/dL for males
 - Platelet count < 100x10⁹/L
 - eGFR < 50 ml/min/1.73m² calculated by Modification to Diet in Renal Disease [MDRD] study equation, unless approved by the Sponsor Medical Monitor (or designee)
6. Diabetes that is not, in the opinion of the investigator, adequately controlled with diet +/- antidiabetic medication
7. Use of any prescription or over-the-counter medications within 7 days prior to vaccination, unless approved by the Sponsor Medical Monitor (or designee).
8. Received immunoglobulins and/or any blood or blood products since completion of the Parent Study.

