10.2 Populations

Safety Population: All subjects who receive Study Drug in ARCT-021-02 only

Longitudinal Safety Population: All subjects who receive Study Drug in either ARCT-021-01 or ARCT-021-02

Immunogenicity Population: All subjects who receive Study Drug in either ARCT-021-01 or ARCT-021-02 and who have evaluable immunogenicity data following first vaccine administration.

Additional populations may be defined for individual immunogenicity endpoints and will be pre-specified in the SAP.

Within these populations, analyses will also include Cohorts that combine relevant safety and immunogenicity assessments across ARCT-021-01 and ARCT-021-02 according to time since administration of last dose of ARCT-021 (See [Table 5](#)). These cohorts are defined as follows.

Two primary cohorts will be defined:

- Cohort 1: ARCT-021-02 vaccinated participants (those participants who receive ARCT-021 in Study ARCT-021-02, including those who were assigned to receive placebo in the parent study (ARCT-021-01) and those who enter the ARCT-021-02 without detectable neutralising antibody responses at baseline)
 - This cohort will be further subdivided for an exploratory analysis of cohorts:
 - Cohort 1a: Primary vaccination (Those participants whose first ARCT-021 vaccine administration occurs in the ARCT-021-02 study) and
 - Cohort 1b: Booster vaccination (Those participants who received primary vaccination in the ARCT-021-01 study and who receive an additional dose of ARCT-021 in the ARCT-021-02 study)
- Cohort 2: ARCT-021-01 vaccinated participants (those participants who were vaccinated with ARCT-021 in the parent study and who do not receive subsequent vaccination with ARCT-021 in the current extension study).
 - This cohort will be further subdivided for an exploratory analysis of subcohorts:
 - Cohort 2a: Those participants who received ARCT-021 7.5 µg dose as a single dose administration in the parent study (Cohorts D1 and D2)
 - Cohort 2b: Those participants who received ARCT-021 10.0 µg dose as a single dose administration in the parent study (Cohort C)
 - Cohort 2c: Those participants who received alternate doses and schedules of ARCT-021 in the parent study (Cohorts A, B)
 - Cohort 2d: Those participants who receive two-dose schedules of ARCT-021 in the parent study (Cohorts E, F, G, H)

Additional analysis cohorts, if required, will be prespecified in the statistical analysis plan.

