5.2 Analysis Sets

The following analysis sets are defined for this interim analysis:

Safety Population: All participants who receive Study vaccine in ARCT-021-02 only.

Longitudinal Safety Population: All participants who receive Study vaccine in either ARCT-021-01 or ARCT-021-02

Immunogenicity Population: All participants who receive Study vaccine in either ARCT-021-01 or ARCT-021-02 and who have evaluable immunogenicity data following first vaccine administration.

Within these populations, analyses will also include Cohorts that combine relevant safety and immunogenicity assessments across ARCT-021-01 and ARCT-021-02 according to time since administration of last dose of ARCT-021. These cohorts are defined as follows.

Two primary cohorts will be defined:

- Cohort 1: ARCT-021-02 vaccinated participants (those participants who receive ARCT-021 in Study ARCT-021-02, including those who were assigned to receive placebo in the parent study (ARCT-021-01) and those who enter the ARCT-021-02 without detectable neutralizing antibody responses at baseline)

This cohort will be further subdivided into additional sub-cohorts for all analyses:

- Cohort 1a: Primary vaccination (i.e., those participants whose first ARCT-021 vaccine administration occurs in the ARCT-021-02 study) and
- Cohort 1b: Booster vaccination (i.e., those participants who received primary vaccination in the ARCT-021-01 study and who receive an additional dose of ARCT-021 in the ARCT-021-02 study). Cohort 1b will be subdivided as follows for data analysis and presentation:
 - Cohort 1b (A): Participants that were in Cohort A (1 mcg single dose younger adult cohort) in the Parent Study
 - Cohort 1b (B): Participants that were in Cohort B (5 mcg single dose younger adult cohort) in the Parent Study
 - Cohort 1b (C): Participants that were in Cohort C (10 mcg single dose younger adult cohort) in the Parent Study
 - Cohort 1b (D1): Participants that were in Cohort D1 (7.5 mcg single dose younger adult cohort) in the Parent Study
 - Cohort 1b (D2): Participants that were in Cohort D2 (7.5 mcg single dose older adult cohort) in the Parent Study

- Cohort 2: ARCT-021-01 vaccinated participants (i.e., those participants who were vaccinated with ARCT-021 in the parent study and who do not receive subsequent vaccination with ARCT-021 in the current extension study). Cohort 2 will be subdivided as follows for data analysis and presentation:

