7.3 Immunogenicity Endpoint Summaries

Participants with evidence of SARS-CoV-2 infection or that received an off-study vaccine will be censored from the immunogenicity analysis for all timepoints and evaluations beyond earlier of the time point at which evidence of SARS-CoV-2 infection occurred or the time point at which off-study vaccine was received. Evidence of SARS-CoV-2 infection includes a positive PCR test or a positive antinucleocapsid antibody test (defined as a concentration $\geq 5,000$ AU/ml)

The timepoints for analysis of each of the immunogenicity parameters is shown in Appendix 9.1.

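### The per-protocol analysis that Protocol 8.9.1 relies on is defined nowhere, so antibody results after immunoglobulin or blood products stay in the immunogenicity summaries by default

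*Protocol*

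**What the plan says.** Protocol 8.9.1 lists disallowed concomitant therapies. They include immunoglobulins and blood products during the study, immunosuppressants (with a corticosteroid dose threshold) and other investigational products. Immunoglobulins, blood products and immunosuppressants used to treat COVID-19 are exempt. The stated consequence is that use does not force withdrawal but may decide "eligibility in the per-protocol analysis". This is the only mention of a per-protocol analysis in either document.

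Protocol 10.2 and SAP 5.2 each define three populations: Safety, Longitudinal Safety and Immunogenicity. The last takes participants who "receive Study vaccine in either ARCT-021-01 or ARCT-021-02 and who have evaluable immunogenicity data following first vaccine administration". Neither document defines evaluable. Protocol 10.2 allows further immunogenicity populations to be pre-specified in the SAP; this SAP adds none.

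SAP 7.3 gives the censoring rule for antibody results: "Participants with evidence of SARS-CoV-2 infection or that received an off-study vaccine will be censored from the immunogenicity analysis", from the earlier of the two events onward. SAP 5.3.3 describes an off-study vaccine as a COVID-19 vaccine other than the study vaccine.

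Exclusion criterion 8 in Protocol 5.2 reads "Received immunoglobulins and/or any blood or blood products since completion of the Parent Study". It stands under the subheading that limits it to subjects who will be dosed in this study.

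**The concern.** The protocol marks certain therapies as able to disqualify a subject from an analysis, but the plan contains no analysis in which that can happen. The secondary objective is the long-term antibody response to ARCT-021. Immunoglobulin or blood products can add donor antibody to a sample, and immunosuppressants can lower the response. If such samples are kept, they are summarised as vaccine response.

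Cohort 2 is the most exposed. Its subjects are not dosed here, so criterion 8 does not apply to them, and one who had immunoglobulin between the studies may still enter. The results are shown by small sub-cohort, where one value can shift a geometric mean.

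**Working it through.** **Tracing the rule through the documents**

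1. Consequence of disallowed therapy: eligibility for a per-protocol analysis (Protocol 8.9.1).
2. Definition of that analysis: none in Protocol 10.2 or SAP 5.2. SAP 4, which lists changes from the protocol's analyses, does not mention dropping one.
3. Population used for antibody results: the Immunogenicity Population (SAP 7), which has no concomitant-therapy condition.
4. Censoring: infection or off-study COVID-19 vaccine only (SAP 7.3).
5. Seroconversion: a 4-fold rise from baseline, with 2-fold as an additional analysis (SAP 4.3, 5 and 7.2), again with no therapy condition.
6. Entry: criterion 8 covers the period before entry, and only for subjects to be dosed here.

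No step removes the sample, so retention is the default.

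**Which results are reached**

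SAP 4.4 and 7.2 limit this interim to Day 1, Day 29 and Day 57 for Cohort 1 and, within this study, to Day 29 for Cohort 2. Cohort 1 is exposed only through use on study. Cohort 2 is exposed through use between the studies or before Day 29. Its Day 197 and Day 281 results belong to the final analysis.

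**Whether use would be known**

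Appendix 1 of the protocol records medications since the Parent Study at screening for all subjects, so use between the studies can be identified. On study, Protocol 8.9.1 requires all medications to be recorded only until 28 days after a dose given here. Otherwise a medication is entered only if linked to an SAE, CESI, NOCD or MAAE, or given for COVID-19.

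**Size, as an illustration**

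The plan states no figure to reproduce. SAP 7.2 computes the GMT as the antilog of the mean log10 titer. If one of n results is multiplied by k and kept, the mean log rises by log10(k)/n, so:

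GMT multiplier = k^(1/n)

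The GMFR changes by the same factor if the baseline value is unaffected. One misclassified subject moves the seroconversion rate by 100/n percentage points.

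For a typical n: SAP 5.2 defines 15 sub-cohorts (1a, five in 1b, nine in Cohort 2). SAP 3.1 gives 106 participants if all enroll, and 106/15 is about 7. Actual sub-cohort sizes are not given, and neither is any fold effect.

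| n | k = 4 | k = 10 | k = 0.1 | Seroconversion, points per subject |
|---|---|---|---|---|
| 7 | 1.22 | 1.39 | 0.72 | 14.3 |
| 10 | 1.15 | 1.26 | 0.79 | 10 |
| 20 | 1.07 | 1.12 | 0.89 | 5 |
| 106 | 1.01 | 1.02 | 0.98 | 0.9 |

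**The case against.** - **The SAP covers an interim only.** A final SAP could still define a per-protocol set, and Protocol 10.2 leaves room for one. This stands. A reader might infer that this plan lets a Cohort 2 subject given immunoglobulin before Day 197 distort the 12-month persistence result. The documents do not support that: Day 197 is outside this interim, and no final SAP is provided.
- **Retention is a default, not a stated rule.** The word evaluable could be used to drop such samples. That is so, but without a definition it would be an unspecified choice made on open-label data, in an analysis meant to support a regulatory filing (SAP 4).
- **The main contaminants are already handled.** Off-study COVID-19 vaccination, which SAP 5.3.3 says occurred in many instances, and infection are both censored. Donor product carrying anti-nucleocapsid antibody might also reach the 5,000 AU/ml threshold in SAP 7.3. That protection would be incidental, and it would record the wrong reason.
- **The analysis is descriptive.** Individual results are listed and the median, minimum and maximum are shown, so an outlier would be visible. This limits the harm, but the reason for the outlier would not be shown beside it.
- **Use between the studies is a separate matter.** Protocol 8.9.1 speaks of the study period, so a defined per-protocol set might not reach earlier use. This is correct, and the censoring rule therefore has to name that period.
- **The multipliers rest on assumptions.** This also stands. An equal split over 15 sub-cohorts is unlikely, since 1a pools all former placebo recipients.

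**Conclusion.** The point holds as a gap between the two documents. The protocol names a safeguard that is never defined, and the SAP's explicit censoring rule leaves out therapies that the protocol itself treats as possibly disqualifying. Followed as written, the plan keeps samples taken after immunoglobulin or blood products not given for COVID-19. Within this interim, that can affect Cohort 2 at Day 29 and Cohort 1 up to Day 57.

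The number of affected subjects is unknown, probably small in healthy adults, and possibly zero. A reader might take 1.39 as an expected bias. It is not: it assumes a 10-fold rise in one subject of a sub-cohort of 7, and neither value is in the documents. At 20 subjects the same rise gives 1.12, and pooled over 106 it gives 1.02.

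A reader might also infer that any steroid course should end a subject's antibody data, as an off-study vaccine does. Nothing in the documents supports an indefinite effect of a short course, so permanent censoring is not justified for that group.

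**What to change.** - **SAP 7.3 and the final SAP:** add receipt of immunoglobulin or blood products, including between the studies, as a censoring trigger from the date of receipt. Show the uncensored summary as a sensitivity analysis.
- **Immunosuppressants at or above the 8.9.1 level, and other investigational products:** keep these subjects in the main analysis. Add a sensitivity analysis that leaves out their later samples. Off-study COVID-19 vaccines stay under the existing rule.
- **Protocol 8.9.1:** replace the reference to a per-protocol analysis with a reference to this rule.
- **Timing:** SAP 5.1 allows no change to the interim SAP after the data pull. If that date has passed, put the rule in the final SAP and label any interim application as post hoc.

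The cost is some wording, one more flag and the loss of a few late samples. The flag relies on screening records and event-linked medication records, so unlinked use more than 28 days after a dose, or during the study in Cohort 2, may be missed. The report should say so.

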8.9.2 Concomitant Procedures

A concomitant procedure is any therapeutic intervention (e.g., surgery/biopsy, physical therapy) or diagnostic assessment (e.g., blood gas measurement, bacterial cultures) performed between signing of the informed consent document and the subject's last protocol-specified study visit.

All concomitant procedures must be recorded in the eCRF until 28 days after the last dose of Study Drug. Thereafter only concomitant medications associated with an SAE or medically attended AE (MAAE) will be entered in the eCRF.

8.10 Treatment Compliance

Compliance with Study Drug dosing is to be monitored and recorded in the eCRF by Study Center staff.

9 SERIOUS AND NON-SERIOUS ADVERSE EVENT REPORTING

9.1 Sponsor Review of Safety Information

Safety information will be collected, reviewed, and evaluated by the Sponsor or designee in accordance with the applicable SOPs throughout the conduct of the clinical trial.

9.2 Regulatory Requirements

The Sponsor or designee is responsible for regulatory submissions and reporting serious adverse events (SAEs), including suspected unexpected serious adverse reactions (SUSARs), to the Investigators per the International ICH guidelines E2A and ICH GCP, as outlined by ICH E6(R2) and subsequent amendments. Country-specific regulatory requirements will be followed in accordance with local country regulations and guidelines.

The Independent Ethics Committee (IEC) or Institutional Review Board (IRB), as appropriate will be notified of any SAE according to applicable regulations.

In addition to the Investigator's assessment of relatedness, the Sponsor or designee will evaluate the available information and perform an independent assessment of all reported SAEs and determine if there is a reasonable possibility that the Study Drug is causally related to a reported SAE. While the Sponsor may upgrade an Investigator's decision it is not permissible to downgrade the Investigator's opinion for the purposes of determining whether the SAE meets the definition of a SUSAR.

For the purpose of regulatory reporting of SUSARs, there are no "expected" AEs in this study population. For Study Drug "expected" AEs, refer to the Reference Safety Information in the Investigator's Brochure.

